## RESEARCH PROTOCOL OUTLINE

**Abstract**

Early adversity exposure profoundly influences diverse aspects of brain and behavioral development and long-term risk for mental and physical illness. Rates of adverse childhood experiences (ACEs) in the United States remain high, with 1 in 6 adults experiencing 4 or more ACEs. Nationwide, numerous efforts have been initiated to reduce rates of ACEs and promote resiliency of high-risk children. One such effort is home visiting (HV), which provides one-on-one coaching to help high-risk parents (e.g., living in poverty, mental health issues) learn skills to promote child development and improve family functioning. Findings on the impact of HV programs have at times been mixed and we have yet to significantly improve psychosocial adjustment of adversity-exposed children. Here we propose to conduct an intervention study to provide in-the-moment parenting tips with the goal of increasing healthy parent-child interactions leading to resiliency in high-risk children. Specifically, in a sample of parents participating in a HV program, we propose to use a smartphone app (mHealth app) to deliver twice-daily tailored messages with tips on monitoring and promoting child development. Daily assessments of parents' emotions, parenting behaviors, and interactions with their children will also be collected via the app. We expect that parents will evidence greater engagement in positive parenting practices on days when they receive the mobile-based parenting tips and strategies relative to on days when they do not receive this content.

**A. Specific Aims**

This is an intervention study to provide in-the-moment parenting tips with the goal of educating parents about monitoring and promoting child development, thereby increasing healthy parent-child interactions leading to resiliency in high-risk children. Specifically, in a sample of parents participating in a HV program, we will use a smartphone app (mHealth app) to deliver twice-daily tailored messages with tips on monitoring and promoting child development. Ecological momentary assessments (EMA) of parents' emotions, parenting behaviors, and interactions with their children will also be collected via the mHealth app. Building off our previous work we expect that parents will evidence greater engagement in positive parenting practices on days when they receive the mobile-based parenting tips and strategies relative to on days when they do not receive this content.

We hypothesize that in-the-moment parenting tips delivered around peak times of parent-child interactions (i.e., before work/school, mealtimes, and bedtime) will promote positive parenting practices in a sample of parents at increased risk of adversity exposure. We aim to use EMA methodology to measure both group level differences (i.e., intervention vs. services as usual) and within-person fluctuations in harsh parenting, children's emotional and behavioral functioning, and positive parenting practices. The study will evaluate the following aims and hypotheses:

**Aim 1. Conduct a 2-arm, randomized, controlled crossover trial to examine the feasibility and effectiveness of a mobile-based parenting app with parents participating in HV services.**

Hypothesis 1a. Parents will report high rates of satisfaction and usability. Hypothesis 1b. Parents will evidence greater engagement in positive parenting practices on days when they receive the mobile-based parenting tips and strategies relative to days when they do not receive this content.

Hypothesis 1c. Groups will evidence increases in positive parenting subscale scores after a month of app engagement.

**Aim 2. Utilize EMA data and follow-up assessments to examine the impact of positive parenting practices on the promotion of child development.**

Hypothesis 2a. Hypothesis 2a. Children will demonstrate less challenging and more positive behavioral functioning on days when their parents receive positive parenting tips.

Hypothesis 2b. Groups will evidence increases in developmental scores after a month of app engagement.

**B. Background and Significance**

**Background:**

**Exposure to early adversity has significant public health implications.** A recent surge of empirical work has focused on how early experiences impact children's developmental trajectories and ultimately the health and well-being of individuals across the lifespan.

This increased attention is in part a result of large-scale epidemiological studies, such as the Adverse Childhood Experiences (ACEs) study, documenting the far-reaching and lasting consequences of childhood adversity on a diverse set of outcomes, including rates of morbidity and mortality. ACEs capture a wide range of potentially traumatic events experienced in childhood (0-17 years), including exposure to violence, abuse, or neglect, witnessing home or community violence, and having a family member attempt or die by suicide. Rates of early adversity in the United States remain high, with 1 in 6 adults experiencing 4 or more ACEs. Moreover, ACEs tend to have a cumulative impact, such that as ACE exposure increases so too does the risk of experiencing negative developmental outcomes. ACEs also place a heavy burden on society, with an estimated annual financial loss of \$748 billion due to criminal justice costs, productivity losses, and mental health services. Overall, these figures underscore ACEs as a pressing public health issue with widespread implications for individuals, families, and society as a whole.

As scientific evidence of the far-reaching consequences of ACEs has increased, so have surveillance efforts at both the state and national level, leading to a better understanding of the burden of childhood adversity and population level differences. More recently, the shift from assessment to action is reflected in policies and practices that focus on increasing awareness of the negative outcomes associated with ACEs, alongside the promotion of strategies that mitigate risk and improve child outcomes and family well-being. Importantly, despite widespread consequences of ACEs, some individuals demonstrate resilience and experience healthy functioning. While less is known about how, and under what circumstances, protective mechanisms and positive experience buffer ACEs, safe, stable, nurturing relationships are key to child health and development. For children and families most at risk, promoting strategies that build

protective capacities is critical to reducing risk and improving outcomes, which in turn can mitigate the societal burden associated with ACEs.

**Influence of positive parenting.** One particularly robust predictor of resilience in the face of adversity is parenting. Parents play a profound role in shaping their children's developmental trajectories. Recently, the National Academy of Sciences, Engineering, and Medicine released *Parenting Matters: Supporting Parents of Children Ages 0–8*, which underscores the importance of quality parenting for child development.

Additionally, Sege and Browne proposed The Healthy Outcomes from Positive Experiences (HOPE) framework, which focuses on promoting positive childhood experiences to prevent or mitigate the effects of ACEs. HOPE identifies four broad categories of positive experiences and their effects on child development, including the need for (1) sustained supportive relationships, (2) growing and learning in safe, stable environments, (3) opportunities for constructive social engagement and connectedness, and (4) social and emotional competencies. Parents play direct and indirect roles in cultivating all four categories. Positive parenting practices are associated with dose-dependent reductions in adult mental health and relational health impairments resulting from ACE exposures. Moreover, positive parenting practices, including engaging the child in reading stories, storytelling/singing, eating meals together, playing with similar-age children, and family outings, are linked with behavioral, emotional, and cognitive improvements in children exposed to adversity. Positive parenting practices are also tied to alterations in brain structure and functioning. For example, shared reading interactions between mothers and their children have been associated with activation in left-sided brain areas supporting expressive and complex language, socio-emotional functioning, and working memory.

**Intervention efforts.** Nationwide, numerous efforts have been initiated to promote positive parenting practices and reduce rates of ACEs in high-risk children. One such effort is home visiting (HV), which provides one-on-one coaching to help high-risk parents (e.g., living in poverty, mental health issues) learn safety, health, and parenting skills to promote child development and improve family functioning. Findings on the impact of HV programs on child development have at times been mixed and we have yet to move the needle on significant improvement in the psychosocial adjustment of adversity-exposed children. Specifically, findings indicate that the potential of HV to improve child developmental outcomes depends in part on the model of HV, the training level of the provider, and the domain of child development in question. Evidence also suggests that the effects of HV on child development may at times be indirect. For example, work by our team found that the association between HV and child development was mediated by the home environment, such that as parents received more home visits, they reported providing more emotional support and cognitive stimulation to their child, which in turn was associated with higher developmental scores for their children. Moreover, the National SafeCare Training and Research Center recently administered an attitudinal survey to SafeCare providers on incorporating mHealth apps into programming. Findings suggested that the vast majority of providers felt that an mHealth app would improve client outcomes and help supplement existing curriculum, however over 70% reported never using an app of any kind (mHealth or otherwise) with their clients. Given the overwhelming public health crisis due to ACEs, the importance of positive parenting practices, and the inconsistent findings on HV's impact on child

development, there is a dire need for low-cost, impactful interventions that can enhance and extend HV to large portions of high-risk families in a consistent and reliable manner. The goal of this project is to test such an intervention.

**Significance:** Despite empirical support for HV models, evidence suggests that HV programs reach on average less than 4% of the population in need of such intervention, particularly low-income families and can be prohibitively costly to bring to scale. Moreover, family engagement and retention in HV services are impeded by life circumstances such as unpredictable or inflexible work schedules, the need for visits outside of the typical work day, and living in other family members who may not want the services. To address these obstacles, service providers and researchers alike are increasingly turning to technology, including mobile health apps, as a means to widespread, low cost service delivery. Mobile health interventions (mHealth) are particularly appealing given their popularity, mobility, and extensive technological capabilities. Crucially, mHealth interventions can bolster service delivery to large numbers of high-risk individuals and families by (1) reaching resource-poor environments, (2) targeting content in an individualized and customized manner, and (3) delivering content at specific times when it is the most relevant and potentially impactful. As such, the project has the potential to develop a much-needed intervention that could be targeted to families receiving HV to bolster the effectiveness of those services, as well as, other at-risk population not involved in HV, but who would similarly benefit from the parenting tips and strategies.

In addition to the service delivery benefits, mHealth apps also allow for researchers to collect extensive data from service recipients via ecological momentary assessment (EMA). EMA has emerged as one of the most promising ways to collect ecologically valid information about temporal and contextual factors that impact behavioral dynamics in real-world settings. EMA involves repeated sampling of participants' current behaviors and experiences in real time, in their natural environments. As such, EMA minimizes recall bias, maximizes ecological validity, and permits the examination of microprocesses that influence behavior in real-world contexts. Through the use of EMA, the proposed study will move beyond examining parenting behaviors as a *static* marker of risk and resilience by testing for a more dynamic or proximal relation between parenting behaviors and developmental outcomes in at-risk children's daily lives. Thus, the study would pilot test a much-needed low cost, far reaching intervention, provide preliminary data on dynamic relations of risk and resilience in high-risk families.

### **C. Preliminary Studies/Progress Report**

The evaluation will be led by the Biomedical and Behavioral Methodology Core (BBMC) of the Department of Pediatrics. The development and implementation consultation will be provided by faculty and staff at the Center on Child Abuse and Neglect (CCAN), which is also housed in the Department of Pediatrics. The BBMC is a shared resource that consists of three primary and three jointly-appointed faculty members, 5 academic support staff and 2 administrative support staff. The BBMC mission is to support and enhance study design, data capture, and analytics for biomedical and behavioral research,

and this Core currently provides a variety of methods support for several ongoing clinical and translational research studies in the Department of Pediatrics as well as several other outside Departments and Colleges. BBMC faculty represent established federally funded scientific researchers with statistics, methods, and informatics expertise and extensive publication records. BBMC faculty and staff offer specialized methods expertise in Bayesian methods, clinical trials, field trials and survey research, study design and management, measurement and psychometrics, analysis of complex sampling designs, generalized linear modeling, generalized latent variable modeling, longitudinal and spatial analysis, time series and dynamic modeling, quantitative genetics, population genetics, computational programming and statistics, software development, database design and management, bioinformatics, and qualitative data methods. Faculty and staff participate in both independent and collaborative research, provide general research consultation, teach and mentor graduate and undergraduate students, and supervise research assistants at all levels of academic and non-academic rank. The BBMC has a strong working relationship with the Center on Child Abuse and Neglect (CCAN). CCAN is a university-based, interdisciplinary center dedicated to the prevention and treatment of child abuse and neglect, and has a long-standing history in the community, state, and nation in conducting clinical implementation and dissemination research on the prevention and treatment services for child maltreatment. As a research group, they have been able to demonstrate the capacity to accommodate reasonable scientific rigor within the demands and realities of services research, along with well-established research-practice partnerships with state authorities and front-line service provider agencies. The overall focus of these collaborations has been to develop, adapt, rigorously test, refine and move to scaled-up implementation with evidence-based child welfare intervention models. The focus has been both on developing or adapting the evidence-based practices (EBPs) themselves and on improving strategies for how these models can be implemented with fidelity at-scale within large public sector child welfare service systems. CCAN team members include established federally funded scientific researchers with extensive publication records, including experience conducting treatment outcome trials in real-world field settings. Funding sources and implementation efforts related to the current demonstration project have included: NIMH (e.g., Effectiveness Trial of SafeCare for Neglect. (NIMH R01MH065667; [name] [PI], [name]); Developing Multi-Component Evidence Based Practice for Child Abuse Service Systems. (NIMH-1R34MH076972; [name] [PI]), Mixed Methods Study of a Statewide EBP Implementation (NIMH R01MH072961; [name] [PI], UCSD; [name], [name], OUHSC); ACYF, Children's Bureau (e.g., State of Oklahoma Title IV-E Waiver Demonstration Project, 2015-2019. [name], lead evaluator, PI of subcontract; Evidence-Based Child Maltreatment Prevention for High Risk Families: Expanding to Latino Communities, Enhancing Family Violence Prevention, and Sustaining Prevention Programs. USDHHS (90CA1764). [name] [PI]); The Centers for Disease Control and Prevention (e.g., Alternatives for Families III. # CCR622338. [name] [PI]); and HRSA (e.g., Maternal, Infant and Early Childhood Home Visiting (MIECHV) Competitive Grant Program, Independent Evaluator subcontract. D89MC23154 [name], PI of subcontract). These projects demonstrate capabilities in evaluating EBP uptake at client, provider, organizational, and systems levels, and use of mixed methods approaches (quantitative/qualitative methods).

#### **D. Research Design and Methods (What, When, How, Where)**

##### **Study Design**

We will use a 2-arm randomized, controlled cross over trial design to evaluate the effectiveness of the mHealth Intervention. We will recruit up to 50 participants from three home visiting programs (SafeCare at NorthCare, Latino Community Development Agency [LCDA], and Parent Child Center [PCCT]). All three of these programs utilize the SafeCare home visiting model, which includes modules on healthy parent-child interactions and promoting parenting skills in high-risk families. We plan to recruit existing and new families in these programs and randomly assign them to receive either 2 weeks of the mHealth intervention + EMA data collection followed by 2 weeks of only EMA data collection or to receive 2 weeks of only EMA data collection followed by 2 weeks of mHealth intervention + EMA data collection. All participants will receive both conditions in counterbalanced order.

Study participation involves consenting to administrative record release and immediate baseline questionnaires assessing demographics, the child's exposure to adversity, parental exposure to childhood adversity, parent's emotional expression, emotion reactivity, and emotion regulation and the child's emotion regulation and development, ecological momentary assessment (EMA) at fixed times twice a day (morning and evenings), and final assessments, which will be the same as the baseline assessments.

**EMA Only Condition** In the EMA only condition, families will continue to receive services utilizing the SafeCare home visiting model, including modules on healthy parent-child interaction and promoting parenting skills in high-risk families, but they will not receive parenting tips via the mHealth app during this period. We plan to administer brief surveys via the mHealth app twice a day at pre-determined times (morning and evening). These surveys will ask parents to provide information about where they are and

with whom, their emotional state, recent parent-child interactions, current stressors or challenges, and their child's emotional and behavioral functioning. Parents will receive these twice daily surveys every day for two weeks.

[figure not shown]
### **mHealth Intervention Condition**

When families are in the mHealth intervention condition, the mHealth app will deliver parenting tips and strategies twice daily for 14 days. Furthermore, we plan to administer brief surveys via the mHealth app twice a day at pre-determined times (morning and evening). These surveys will ask parents to provide information about where they are and with whom, their emotional state, any recent parent-child interactions, and any current stressors or challenges. Parents will receive these twice-daily surveys and the parenting tips for every day for two weeks.

Of note, during the 4-week EMA study, parents will receive either 2 weeks of the mHealth intervention + EMA data collection followed by 2 weeks of only EMA data collection or to receive 2 weeks of only EMA data collection followed by 2 weeks of mHealth intervention + EMA data collection.

The order of mHealth intervention and EMA data collection will be counterbalanced across participants to allow for a within-subjects comparison.

See the study diagram below for a visual depiction of our data collection schedule.

**Figure 1: Proposed Study Design**

## Research Questions

This investigation will: (1) test a low-cost, far reaching, evidence-based intervention delivered via mHealth app technology, (2) examine the effectiveness of a mHealth app intervention at improving positive parenting practices, and (3) investigate within and between person differences via EMA thereby strengthening causal implications. This data will be used to inform the following key study questions:

Research Question 1: How effective and feasible is a mobile-based parenting app intervention for parents participating in Home Visiting services.

Research Question 2: What is the impact of positive parenting practices on the promotion of child development?

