## **I. Statistical Methods**

### **Data Analysis**

**Analyses.** Analyses will be guided by Drs. [name] (Quantitative Psychologist) and [name] (Biostatistician).

For **Hypothesis 1a** we will analyze the satisfaction and usability responses gathered at the post-intervention, follow-up assessment using descriptive and inferential statistics. Descriptively, we will report central tendency (means, medians) and dispersion (standard deviation, interquartile range) measures for response distributions. To evaluate the significance of app appeal, we will conduct one sample Wilcoxon signed rank tests to determine if the central location of the data departs from point values that reflect slight or minimal satisfaction/usability.

Additionally, analysis of the qualitative focus group transcription will be completed using NVivo software. Broad themes within the transcription will be identified using a template approach. [name] (qualitative contractor) will code a sample and develop a specific codebook. Reliability will be established between [name] and one of her graduate students. Themes identified from the focus group will be used to update and finalize the mHealth app for future grants and studies.

**Hypothesis 1b** will involve mixed effects model analyses where positive parenting outcomes are regressed on a Tips indicator (tips delivered vs tips not delivered), a period indicator, and a random intercept term. The period indicator will assess outcome variability associated with the first two weeks vs the last two weeks of app engagement. An interaction term between the Tips factor and period factor will also be examined to determine if the intervention effect differs by order of presentation. We expect that parents will evidence greater engagement in positive parenting practices on days when they receive the mobile-based parenting tips and strategies relative to on days when they do not receive this content. Assuming no Tips by period interaction, the focal effect for testing this hypothesis will be the main effect of Tips Delivered.

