**Hypothesis 1c** will be tested using a mixed effects model analysis where parenting subscale scores at baseline and post-intervention are regressed on an assessment time indicator, a randomization condition indicator, and a random intercept term. Assuming no interaction between assessment time and randomization group, the focal effect is the main effect of assessment time, which represents the pre-to-post difference in parenting scores.

**Hypothesis 2a** will be analyzed in the same manner as Hypothesis 1b replacing the parenting outcomes with child challenging and positive behavior counts. The hypothesis of behavioral improvement during weeks where parents receive tips will be tested by focusing on the main effect of the Tips indicator.

Finally, **Hypothesis 2b** will be analyzed in the same fashion on Hypothesis 1c. We hypothesized the child development scores will increase at the post-intervention assessment and this will be evaluated by testing the main effect of assessment timing.

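### Aim 2 and Research Question 2 ask how positive parenting relates to child outcomes, but no planned model has parenting as a predictor

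*Combined protocol and SAP*

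**What the plan says.** Section A states Aim 2 as using the EMA and follow-up data to "examine the impact of positive parenting practices on the promotion of child development". Section D, Research Questions, repeats this as the second of two key questions: "What is the impact of positive parenting practices on the promotion of child development". The Significance part of section B justifies EMA partly by the wish to study parenting as something that varies from day to day with the child's outcomes, not as a fixed marker of risk. In all three places parenting is the exposure and the child is the outcome.

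The two hypotheses under Aim 2 name other exposures. Hypothesis 2a expects better child behavior "on days when their parents receive positive parenting tips". Hypothesis 2b reads: "Groups will evidence increases in developmental scores after a month of app engagement".

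Section I, Data Analysis, specifies the models:

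- Hypothesis 1b: "positive parenting outcomes are regressed on a Tips indicator (tips delivered vs tips not delivered), a period indicator, and a random intercept term", with a Tips-by-period interaction also examined.
- Hypothesis 1c: parenting subscale scores are "regressed on an assessment time indicator, a randomization condition indicator, and a random intercept term".
- Hypothesis 2a: it "will be analyzed in the same manner as Hypothesis 1b replacing the parenting outcomes with child challenging and positive behavior counts". The focal effect is the Tips main effect.
- Hypothesis 2b: it follows Hypothesis 1c with the developmental score as outcome, and "this will be evaluated by testing the main effect of assessment timing".

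**The concern.** A reader who goes from Research Question 2 to the analysis section expects a model with the child outcome on the left and a parenting measure on the right. There is none. If the plan is followed exactly, the study will report what the tips did to child behavior and how developmental scores moved over a month. It will say nothing direct about how parenting and child functioning go together.

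Two things are at stake. First, one of two key questions, and part of the stated reason for using EMA, would go unaddressed although the relevant measures are collected. Second, the only Aim 2 results available would be a tips effect and a time effect, reported under a question about parenting. Section H says the results will serve as pilot data for grant applications, so the label on each estimate matters.

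**Working it through.** **1. Where parenting enters each model (section I, Data Analysis).**

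- H1b: outcome is EMA positive parenting; predictors are Tips, period and Tips x period.
- H1c: outcome is the parenting subscales; predictors are assessment time and randomization condition.
- H2a: outcome is child behavior counts; predictors are Tips, period and Tips x period.
- H2b: outcome is the developmental score; predictors are assessment time and randomization condition.

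All four have a random intercept. Parenting is an outcome twice and a predictor never. Data Sources and section E mention possible mediators and moderators as things to measure, but no mediation, moderation or lagged model follows. The predictive analysis under Administrative Data concerns app use.

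**2. Are the data there?** Section E, Quantitative procedures, gives the Alabama Parenting Questionnaire and the Developmental Profiles-4 at baseline and follow-up, and at least one shortened measure per construct in the EMA. The EMA data section lists both parent-child interactions and child functioning. One loose end: the survey content listed for the mHealth Intervention Condition does not mention child functioning, while the EMA Only Condition does.

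**3. The plan's own power figures.** With d_z = g / sqrt(2(1 - r)), two-sided alpha 0.05 and 80% power, the exact paired t-test gives:

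- r = 0.40: d_z = 0.35/1.095 = 0.320, n = 79; d_z = 0.55/1.095 = 0.502, n = 34.
- r = 0.60: d_z = 0.35/0.894 = 0.391, n = 54; d_z = 0.55/0.894 = 0.615, n = 23.

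All four stated sizes reproduce. They cover within-group differences only; no parenting-to-child association is powered.

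**4. Can the planned estimates stand in for the missing one?** An illustrative crossover was simulated with 2,000 parents, 14 days per period, unit-variance random intercepts and daily errors, and no confounding. The Tips effect on parenting was 0.5. The total Tips effect on the child, 0.5 x slope + direct effect, was held at 0.30. These values are assumptions, not figures from the documents.

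| True slope | Direct effect | Planned: Tips on parenting | Planned: Tips on child | Added model: parenting on child | Added model: Tips given parenting |
|---|---|---|---|---|---|
| +0.6 | 0 | 0.50 | 0.29 | 0.60 | -0.01 |
| 0 | 0.3 | 0.50 | 0.31 | 0.00 | 0.30 |
| -0.4 | 0.5 | 0.51 | 0.29 | -0.40 | 0.49 |

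The planned estimates are the same, apart from simulation noise, whether parenting helps, does nothing or harms. The last column shows why parenting must not be added to the H2a model itself: the Tips coefficient then stops being the total randomized effect of 0.30 and moves between -0.01 and 0.49.

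**5. What a between-person analysis could detect.** By Fisher's z, the detectable r is tanh((1.960 + 0.842)/sqrt(n - 3)). For n = 50 this is tanh(2.802/6.856) = 0.39. With 40 or 30 completers (assumed numbers) it is 0.43 or 0.49. At n = 50, power is 28% for r = 0.2, 56% for r = 0.3 and 83% for r = 0.4.

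**The case against.** The strongest reply is that Aim 2 is given its working meaning by Hypotheses 2a and 2b, and the models test both as worded. That stands: no stated hypothesis lacks a test, and the gap lies between the hypotheses and the aim and question above them.

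A second reply is that randomized tips are the study's lever on parenting, so Hypotheses 1b and 2a together give indirect evidence. They show whether tips move parenting and whether tips move the child. As step 4 shows, they do not show whether the second follows from the first.

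A third reply is that an added model cannot deliver impact either, because parenting is not randomized and the same parent reports both variables. This also stands. It is why rewording is needed even if the model is added.

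Three stronger readings are tempting and not supported:

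- A reader might infer that the study is unable to answer Research Question 2. The limit is in the planned analyses, not in the data.
- A reader might infer that a null Hypothesis 2a will be reported as parenting having no effect. The plan does not say so; it frames that test as a comparison of weeks with and without tips.
- A reader might infer that Hypothesis 2a is far weaker than a direct within-person test of parenting. The documents give no within-person slope, standard deviation, intraclass correlation or response rate. They also conflict on survey frequency: twice daily in section D, once daily in section E, Quantitative procedures. No such comparison can be based on them.

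**Conclusion.** The point holds as a mismatch between question and analysis. Research Question 2 and Aim 2 are about parenting as exposure, every planned child-outcome model is about tips or time, and following the plan leaves the question unanswered. This rests on reading the models and needs no numerical assumption. The simulation only illustrates it, with assumed effects and no confounding.

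The planned Hypothesis 2a and 2b analyses are not put in doubt by this point. The within-person power of an added model cannot be computed from the documents. For a between-person analysis, 0.39 is a best case, because 50 is the maximum recruitment and assumes no attrition.

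**What to change.** 1. Keep the Hypothesis 2a and 2b models unchanged, so that the Tips main effect remains the total randomized effect.
2. Add a separate, pre-specified model of EMA child behavior on EMA positive parenting. Split parenting into the parent's own mean and the deviation from it, and adjust for Tips and period with a random intercept. As a sensitivity analysis, use the previous survey's parenting score. Label the result a non-randomized, single-reporter association, and do not read the Tips coefficient from this model as the test of Hypothesis 2a.
3. If wanted, relate change in the Positive Parenting subscale to change in the developmental score, as exploratory only, stating the detectable correlation of about 0.39.
4. Whether or not the model is added, reword Aim 2 and Research Question 2 to match what is estimated: effect of tips on child outcomes (Hypothesis 2a), pre-post change (Hypothesis 2b) and, if the model is included, association of parenting with child outcomes.
5. Confirm that child functioning is surveyed in both conditions, and reconcile the once-daily and twice-daily descriptions, since these define the records and the lag for the added model.

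The cost is some analysis text and one further model on data already planned. No new collection is needed if item 5 is confirmed. The downside is that the answer on parenting will be associational, not causal.
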